3.3. STUDY INSURANCE

Before the start of the study the sponsor-investigator and principal investigator of each site will ensure that adequate insurance for patients is in place covering losses due to death or injury resulting from the study, in accordance with applicable laws and regulations in each country where the trial is conducted (Finland, Sweden). Adequate insurance for investigators and study staff will be ensured. The pharmaceutical company supplying drugs used in the study must have their own liability insurance.

4. INVESTIGATIONAL PLAN Study design and duration

This is an investigator initiated, academic, non-randomized, open-label multicenter phase 2 study for patients with multiple myeloma in relapse or progression after 1 to 3 prior treatment lines and in need of therapy.

All patients will receive successive cycles of CAR + ELO + Dex according to the schedule shown in Table 2 and 6. Cycles are to be continued until progression, relapse or excess toxicity. The primary objective is to assess the overall response rate obtained with the regimen. This study will have phase 2a portion with 40 included patients to show the feasibility and safety of this design and if observed will be expanded to phase 2b portion with additional number of patients based on statistical power calculations..

4.1 Study procedures:

At registration each patient will have an unique identification number and following details will be documented:

- Name of study center and responsible investigator
- Date of birth of study patient
- Date of signed informed consent

Helsinki University Hospital Comprehensive Cancer Center Hematology
Clinical study protocol NMSG#24/15

- Date of treatment start

The study patient is considered enrolled on first day of study protocol treatment. Any study related investigations are not started before written informed consent.

- At inclusion: before the start of protocol treatment blood- and urine values within 2 weeks before study start, bone marrow samples within 4 weeks and bone imaging within 2 months
- During treatment: within 5 days before next cycle
- At progression and if patient is taken/withdrawn off protocol

All patients will be followed until 3 years after onset of the treatment protocol.

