ELO will be given on cycle days 1 and 15.

Dexamethasone as in cycles 1-2.

Cycles 9 -

CAR, ELO and Dex will be given on days 1 and 15 from cycle 9 until relapse or progression or excess toxicity.

Duration of Study:

Expected duration of treatment:

- patient recruitment 24 months
- primary endpoint (ORR) together with the relevant secondary endpoints will be assessed after the minimum follow-up of one year has been reached with the last included patient
- to assess PFS and TTNT all patients will be followed until 4 years after first dose

Helsinki University Hospital Comprehensive Cancer Center Hematology
Clinical study protocol NMSG#24/15

LIST OF ABBREVIATIONS AND GLOSSARY OF TERMS

Common abbreviations used in oncology protocols are provided below. Program-specific or protocol-specific abbreviations must be added to this list, and unnecessary abbreviations removed, as applicable. Abbreviations that are retained should not be changed.

Abbreviation	Term
AE	adverse event
AFOS	alkaline phosphatase
ALT, ALAT	alanine aminotransferase
ANC	absolute neutrophil count
API	active pharmaceutical ingredient
ASCO	American Society of Clinical Oncology
ASCT	Autologous stem cell transplantation
ASO-RQ	Allele specific oligonucleotide real-time quantification
AST	aspartate aminotransferase
AUC	area under the plasma concentration versus time curve
AUC _{24 hr}	area under the plasma concentration versus time curve from zero to 24 hours
AUC _{inf}	area under the plasma concentration versus time curve from zero to infinity
AUC _τ	area under the plasma concentration versus time curve from zero to next dose
BID	bis in die; twice a day
BM	bone marrow
BSA	body surface area
BUN	blood urea nitrogen
BZM	Bortezomib
CBC	complete blood count
CL	clearance, IV dosing
CL _p	plasma clearance
CL _{Total}	total clearance
C _{max}	single-dose maximum (peak) concentration
CNS	central nervous system
CR	complete remission
CrCl	Creatinine Clearance
CRO	Clinical trial research organization
CRP	C-reactive protein
CT	computed tomography

Helsinki University Hospital Comprehensive Cancer Center Hematology
Clinical study protocol NMSG#24/15

Abbreviation	Term
CY	Cyclophosphamide
CYP	cytochrome P ₄₅₀
DDI	drug-drug interaction
DLT	dose-limiting toxicity
DME	drug metabolizing enzymes
DNA	deoxyribonucleic acid
DSRT	Drug sensitivity and resistance testing
ECG	Electrocardiogram
ECOG	Eastern Cooperative Oncology Group
eCRF	electronic case report form
ELISA	enzyme-linked immunosorbent assay

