5.2.1 DOSE MODIFICATION GUIDELINES FOR CARFILZOMIB

In a case of study related adverse event the clinical investigator must assess its possible relationship to carfilzomib in addition to elotuzumab and dexamethasone.

Table 7. Carfilzomib dose reduction guidelines for toxicity and dose modification			
	1 st dose reduction	2 nd dose reduction	3 rd dose reduction
70 mg/m ²	56 mg/m ²	45 mg/m ²	36 mg/m ²

The basic principle is that if a patient requires an interruption of carfilzomib of more than four weeks this study patient will be removed from study; all exceptions to this must be discussed with principal investigator. If the carfilzomib dose is reduced once, it will be continued for at least one cycle. In case of excellent toleration of this cycle, the dose level prior to reduction may be resumed by the investigator's discretion.

Table 8.

Carfilzomib dosing guidelines for treatment- emergent hematologic toxicity

Hematologic toxicity	Recommended action
Thrombocytopenia	
If platelets $\leq 30 \times 10^9/l$	If $10-30 \times 10^9/l$ without bleeding continue the same dose If evidence of bleeding or platelets $< 10 \times 10^9/l$, withhold dose until platelets return to $\geq 10 \times 10^9/l$ and/or bleeding is controlled, then resume the same dose
For each subsequent drop to $\leq 30 \times 10^9/l$	If $10-30 \times 10^9/l$ without bleeding continue at the same dose If evidence of bleeding or platelets $< 10 \times 10^9/l$, withhold dose until platelets return to $\geq 10 \times 10^9/l$ and/or bleeding is controlled, then resume at 1 dose reduction.
Neutropenia	
If ANC $\leq 0.75 \times 10^9/l$	If ANC $0.5-0.75 \times 10^9/l$, continue at the same dose If ANC $< 0.5 \times 10^9/l$, withhold dose until ANC returns to $\geq 0.5 \times 10^9/l$, then resume at the same dose.
For each subsequent drop to $\leq 0.75 \times 10^9/l$	If ANC $0.5-0.75 \times 10^9/l$, continue at the same dose If ANC $< 0.5 \times 10^9/l$, withhold dose until ANC returns to $\geq 0.5 \times 10^9/l$, then resume at 1 dose reduction
Neutropenic fever	If ANC $< 0.5 \times 10^9/l$, and single temperature $> 38.5^\circ\text{C}$ or temperature $> 38.0^\circ\text{C}$ more than one hour, withhold dose until ANC returns to baseline level, then resume at the same dose.

ANC = absolute neutrophil count.

Helsinki University Hospital Comprehensive Cancer Center Hematology
Clinical study protocol NMSG#24/15

Conditions not requiring dose reduction of carfilzomib

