- Grade 3 nausea, vomiting or diarrhea, unless persisting more than 3 days with adequate treatment of antiemetics or antidiarrheal agents
- Grade 3 dexamethasone-related hyperglycemia
- Grade 3 fatigue, unless persisting for > 14 days
- Alopecia

Table 9. Carfilzomib dosing guidelines for nonhematologic toxicity

Nonhematological toxicity	Recommended action
Renal dysfunction	
Serum creatinine equal to or greater than 2 x baseline, or CrCl < 15 ml/min, or decreases to ≤ 50% of baseline or need for dialysis	Withhold dose and continue monitoring the renal function If attributable to carfilzomib, resume when renal function has recovered to within 25% of baseline, start at 1 dose level reduction If not attributable to carfilzomib, dosing may be resumed at the discretion of the physician Patient will be withdrawn from study in case of permanent dialysis need
≥ grade 3 elevation in liver function tests	Withhold dose and resume at 1 dose reduction level when toxicity has recovered to baseline
Grade 3 infection	Withhold carfilzomib until infection resolves and resume at the same dose
Congestive heart disease	Any subject with symptoms of congestive heart failure, whether or not drug related, must have the dose held until return to baseline, after which treatment may continue at a reduced dose, or consider discontinuation of study protocol. If no recovery in 4 weeks, patient must be withdraw.
Left ventricular ejection fraction	
For resting LVEF < 40% or reduction of LVEF to < 55% if the drop is greater than 20% form baseline	Withhold until LVEF returns to > 40% or, if held due to a drop to < 55%, to within 15% of baseline and resume at 1 dose reduction.
Other grade 1 or 2 nonhematologic toxicity	Continue at the same dose
Any other drug-related nonhematologic toxicity ≥ grade 3	If attributable to carfilzomib, withhold dose Resume at 1 dose reduction when toxicity has resolved to grade 2 or less or to baseline If tolerated, the reduced dose may be escalated to the previous dose at the discretion of the physician
PRES: posterior reversible encephalopathy syndrome; headache, altered mental status,	Stop carfilzomib and study treatment and the patient is withdrawn from study. In visual or

Helsinki University Hospital Comprehensive Cancer Center Hematology
Clinical study protocol NMSG#24/15

seizures, visual loss, hypertension	neurological symptoms	neuroradiological imaging is recommended.
-------------------------------------	-----------------------	---

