9.2 STATISTICAL AND EFFICACY ANALYSES

Statistical analyses will be performed on intention-to-treat and on per-protocol-treated principle. Patients who have been included in the study but been withdrawn before any study drug administration are not included in analyses. Safety and efficacy analyses will be done for all patients who have received at least a single dose of study drug. Any spurious data will be abandoned. Missing

Helsinki University Hospital Comprehensive Cancer Center Hematology
Clinical study protocol NMSG#24/15

data will be handling as missing data not with replacing it with a median parameter number.

Efficacy analyses will be done using International Myeloma Working Group response criteria (Appendix 5). Response will be assessed before each cycle. Progression will be assessed using IMWG criteria for progressive disease.

For classification the adverse events NCI CTCAE version 4.0 will be used. Threshold for safety of this CAR-ELO-Dex combination is considered to be less than 70% of grade ≥ 3 non-hematological adverse events.

Efficacy, safety and QoL analysis will be performed when last patient in has been treated for two years in the study. Kaplan-Meier method will be used to estimate the time to event analyses. The PFS, TTNT and duration of response will be calculated from the start of the first dose of study drug combination.

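### The synopsis follows patients for PFS and TTNT to 4 years and Section 4.1 to 3 years, and the protocol does not say whether patients taken out of the study for toxicity stay in follow-up

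*Protocol*

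**What the plan says.** **Follow-up length.** The synopsis, under Duration of Study, says: "to assess PFS and TTNT all patients will be followed until 4 years after first dose". Section 4.1 says: "All patients will be followed until 3 years after onset of the treatment protocol".

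**Time origin and method.** Section 9.2 says: "The PFS, TTNT and duration of response will be calculated from the start of the first dose of study drug combination". It also says: "Kaplan-Meier method will be used to estimate the time to event analyses". It states no censoring rule.

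**Leaving the study for toxicity.** Section 5.2.1 says, as a basic principle: "if a patient requires an interruption of carfilzomib of more than four weeks this study patient will be removed from study". Exceptions are to be discussed with the principal investigator. Table 9 says of renal dysfunction: "Patient will be withdrawn from study in case of permanent dialysis need". It says of posterior reversible encephalopathy syndrome (PRES): "Stop carfilzomib and study treatment and the patient is withdrawn from study". The heart-failure row requires withdrawal if there is no recovery in 4 weeks, but does not say from what.

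**What happens next.** Section 4.2.3 asks for an end-of-study assessment at withdrawal and does not replace the patient. The last column of Table 1 is End of study. Section 4.2.4 lets a patient continue on the remaining one or two drugs when one drug is permanently stopped.

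**The concern.** Two follow-up lengths are fixed for the same two secondary endpoints. A site working from Section 4.1 would stop collecting data a year before the horizon that the synopsis sets. A later analysis plan cannot repair this, because it cannot analyse data that sites were not told to collect.

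The second part concerns wording. The protocol does not separate leaving study treatment from leaving the study. TTNT is the endpoint most exposed. Section 5.4.3 bars other antimyeloma therapy during the study, and Section 5.4 has concomitant therapies reported only until 30 days after the last dose, so the next line of treatment will usually fall outside the data collection that the protocol describes. If removal also ended follow-up for progression, PFS would lose events. Its Kaplan-Meier estimate would depend on removed patients having the same hazard as those who stay.

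**Working it through.** **1. Do the two horizons really conflict?** The synopsis counts from first dose and Section 4.1 from the onset of protocol treatment. Section 4.1 also counts a patient as enrolled on the first day of protocol treatment, so these are the same day, and Section 9.2 starts PFS and TTNT there. Both sentences cover all patients. The difference is 48 − 36 = 12 months.

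**2. Is there a stated figure to reproduce?** Not for PFS or TTNT: the protocol gives no expected median, event count or precision for either. Its only calculated figure is the 95% interval of 53-83% for an expected ORR of 70% with N = 40. The exact (Clopper-Pearson) interval for 28/40 is 53.5-83.4%, which agrees, but it has no bearing on follow-up.

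**3. PFS events lost at the shorter horizon.** Inputs: N = 40, and median PFS taken from regimens cited in the protocol. These are 9.7 months (elotuzumab + bortezomib + dexamethasone, Section 1.7), 18.7 months (carfilzomib + dexamethasone, Section 1.4.2) and 26.3 months (carfilzomib + lenalidomide + dexamethasone, Section 1.4.2). Using them for this regimen is an assumption. With exponential PFS and every patient followed to the full horizon:

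expected events by month t = 40 × (1 − 0.5^(t/median))

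| Median (months) | PFS at 36 | PFS at 48 | Events by 36 | Events by 48 | Lost |
|---|---|---|---|---|---|
| 9.7 | 0.076 | 0.032 | 36.9 | 38.7 | 1.8 |
| 18.7 | 0.263 | 0.169 | 29.5 | 33.2 | 3.8 |
| 26.3 | 0.387 | 0.282 | 24.5 | 28.7 | 4.2 |

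(Losses come from unrounded values.) Each median lies below 36 months, so the lost events are all in the tail. TTNT cannot be sized, because the protocol gives no TTNT figure.

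**4. Who is taken out of the study?** Three rules use explicit wording: carfilzomib interruption beyond four weeks (with exceptions), permanent dialysis and PRES. A permanent stop of carfilzomib is also an interruption of more than four weeks, so Section 4.2.4 (continue on the other drugs) and Section 5.2.1 (leave the study) can both apply to one patient.

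**5. What if removal did end follow-up?** This was simulated with exponential PFS (median 18.7 months before removal), exponential removal, and a 48-month horizon. Patients were either followed through or censored at removal. Removal rates and hazard ratios are assumptions; the protocol gives none.

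| Removed per year | Hazard ratio after removal | True median | KM median if censored at removal | Events of 40, followed | Events of 40, censored |
|---|---|---|---|---|---|
| 10% | 1 | 18.7 | 18.7 | 33.3 | 28.8 |
| 10% | 1.5 | 18.1 | 18.7 | 34.1 | 28.7 |
| 10% | 2 | 17.6 | 18.7 | 34.5 | 28.8 |
| 20% | 1 | 18.7 | 18.6 | 33.2 | 24.8 |
| 20% | 1.5 | 17.5 | 18.7 | 34.8 | 24.8 |
| 20% | 2 | 16.6 | 18.6 | 35.6 | 24.8 |
| 30% | 1 | 18.7 | 18.7 | 33.3 | 21.3 |
| 30% | 1.5 | 17.0 | 18.7 | 35.3 | 21.3 |
| 30% | 2 | 15.9 | 18.7 | 36.4 | 21.3 |

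With an unchanged hazard, events are lost but the median is not biased. With a hazard 1.5 to 2 times higher after removal, the Kaplan-Meier median is too high by about 0.6 months (18.7 − 18.1) to 2.8 months (18.7 − 15.9).

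**The case against.** The 3- versus 4-year conflict has no good answer. Its effect, however, is modest: stopping everyone at 36 months leaves the curve up to 36 months unchanged and adds no bias. These are also secondary, descriptive endpoints in a single-arm study. That stands.

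The case on removal is stronger. Both follow-up sentences say all patients, and in Section 4.1 the sentence comes straight after the assessments for patients taken off protocol, so it can be read to include them. Section 4.2.3 is headed as discontinuation from treatment although its text speaks of the study, which suggests loose wording rather than an intention to stop follow-up. Section 3 asks for observations to be completed as far as possible at withdrawal, and Section 7.3 has SUSARs reported for a year after the last dose, so the end of treatment does not end all data collection. TTNT needs the date of the next therapy, not a visit column. The schema in Table 2 could not be read here and may show a follow-up phase.

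A reader might infer that every patient stopped for toxicity leaves the study, that TTNT cannot be observed in them, and that the Kaplan-Meier curves are informatively censored. The documents do not support that. Section 5.2.1 allows exceptions, Section 4.2.4 allows continuation on the remaining drugs, the heart-failure row does not mention the study, and no censoring rule is stated. A count such as 4 to 8 of 40 patients censored this way would rest only on an assumed 10-20% removal rate. What survives is that the sections can be read either way and the schedule provides for nothing after End of study.

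**Conclusion.** The contradiction on follow-up length is exact and unresolved. It concerns about 2 to 4 late PFS events of 40 (1.8 to 4.2), given exponential PFS, medians of 9.7 to 26.3 months and full follow-up to each horizon. It touches neither ORR nor, in these scenarios, the median PFS.

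The removal wording is a real inconsistency with a conditional consequence. Events are lost only if follow-up stops at removal, and bias arises only if removed patients also have a different hazard. The protocol states neither condition, so the losses and biases in step 5 show what is at risk, not what will occur. Both parts merit correction, because follow-up that is not collected may be impossible to recover.

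**What to change.** - **Section 4.1:** state one horizon, the 4 years from first dose that the synopsis ties to PFS and TTNT.
- **Sections 4.2.3 and 5.2.1 and Table 9:** state that patients off study treatment remain in follow-up for progression, next therapy and death unless they withdraw consent.
- **Table 1:** add a follow-up column for these three items.
- **Sections 4.2.4 and 5.2.1:** the sponsor should reconcile the two on a patient whose carfilzomib is stopped. The treatment-stopping rules themselves need no change for this point.

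The cost is a protocol amendment and some post-treatment data, largely available from routine care, over a period that the synopsis already promises to cover.

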4.2 STUDY POPULATION

4.2.1 Inclusion criteria

Each patient must meet all of the following inclusion criteria to be enrolled in the study:

1. Male or female patients at the age of 18 to below 75 years with the life expectancy of at least three months.
2. Prior confirmed diagnosis of multiple myeloma and measurable disease in blood or urine with at least one of the following: Serum M-protein $\geq 5\text{g/l}$, Urine M-protein $\geq 200\text{ mg/24 hours}$, In subjects without detectable serum or urine M-component, serum free light chain (S-FLC) $> 100\text{ ml/l}$ (involved light chain) and an abnormal serum kappa/lambda ratio
3. Relapse or progression after 1 to 3 prior treatment lines, which have included proteasome inhibitors (bortezomib, carfilzomib and/or ixazomib) and/or lenalidomide. Refractoriness to bortezomib, ixazomib and/or lenalidomide is allowed in the preceding cycle. Patients with previous autologous transplantation can be included.
4. Need of treatment of relapse or progression: IMWG criteria for relapse/progression (paraprotein or CRAB criteria or both). (Appendix 5)
5. Voluntary written consent must be given before performance of any study related procedure not part of standard medical care, with the

Helsinki University Hospital Comprehensive Cancer Center Hematology
Clinical study protocol NMSG#24/15

understanding that the patient may withdraw consent at any time without prejudice to future medical care.

6. Females of childbearing potential (FCBP) must have a confirmed negative serum pregnancy test within the 7 days prior to inclusion
7. Females of childbearing potential must use one effective method of contraception and their partners condom during the study and for 120 days following the last study drug treatment dose and male subjects who are sexually active with FCBP must agree to use condom during the study and for 180 days following the last study drug treatment dose.
8. Eastern Cooperative Oncology Group (ECOG) performance status 0-2, or Karnofsky at least 60. (Appendix 1)
9. Patients must meet the following adequate organ and bone marrow function within 21 days prior to inclusion:
 - Absolute neutrophil count (ANC) $1,000/\text{mm}^3$ ($\geq 1.0 \times 10^9/\text{L}$) and platelet count $75 \times 10^9/\text{L}$. Platelet transfusions to help patients meet eligibility criteria are not allowed within 3 days before study enrollment. Granulocyte growth factors are allowed to meet the inclusion criteria.
 - Hemoglobin (Hb) $\geq 80 \text{ g/l}$ (use of erythropoietin and red blood cell transfusions allowed by institutional guidelines, however the most recent RBC may not have given within 7 days prior to obtaining screening Hb)
 - Total bilirubin < 1.5 times the upper limit of the normal range (ULN).
 - Alanine aminotransferase (ALT) and aspartate aminotransferase (AST) < 3 times the ULN.
 - Calculated creatinine clearance $\geq 40 \text{ mL/min}$ (Cockcroft-Gault estimation of creatinine clearance (CRcl): $\text{CRcl (mL/min)} = (140 - \text{age}) \times (\text{weight [kg]}) / 72 \times (\text{serum creatinine [mg/dL]})$; for females, multiply by 0.85 (Cockcroft DW. 1976, Luke DR. 1990)(Appendix 2).
10. Patient must be willing and able to adhere to the study protocol visit schedule and other protocol requirements.

11. Negative pregnancy test at inclusion if applicable

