TTNT	Time to next treatment
UK	United Kingdom
ULN	upper limit of the normal range
US	United States
VGPR	Very good partial remission
VTE	Venous thromboembolism
WBC	white blood cell
WHO	World Health Organization

[figure not shown]
Helsinki University Hospital Comprehensive Cancer Center Hematology
Clinical study protocol NMSG#24/15

Table 1. Schedule of study investigations

	Screening	Cycles 1- until end of study, D1 (lab within 5 days before)	Cycles 1-8, D8 D15, D22* (lab within 3 days)	Cycles 1-8 D15	Cycles 9-, D15 until end of study (lab in 3days)	End of study
Medical history	X					
Physical examination + neurool.evaluation	X	X	X**			X
Vital signs	X	X	X*		X	X
Hematology	X	X				X
Immunochemistry	X	X				X
Blood chemistry	X	X				X
Pvk+neut+tromb, K,Na,krea,alat, afos,bil (safety lab*)			X*		X	
Safety assessment, AEs	X	X	X*		X	X
BM aspiration+ 8-color EuroFlow	X		X (when VGPR has achieved, repeated if VGPR/CR and after 1 year if VGPR/CR)			
Bm-MM-FISH	X					
Bone imaging	X					
ECG (a)	X					
Thorax x-ray	X					
Cardiac ECHO	X					
Biobank	X			In CR and at relapse		
Samples to FIMM in Finland	Finland			Bm + blood at relapse		
Pregnancy test (b)	X	X (b)				
Quality of Life		X		X		X

a) ECG in C1-2, D1, thereafter if clinically needed. b) Pregnancy testing must be performed at the beginning of each 28-day cycle and at the end of study visit, applying to women of childbearing potential. * Vital signs not needed on D22 and after C2 Safety lab and AEs on D22 if clinically needed. ** Physical examination if needed due to clinical symptoms.

Table 2. Study schema

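### The platelet-transfusion ban is counted from the first dose, not from the qualifying count, and sections 4.1 and 4.2.1 give different age limits for eligibility blood values

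*Protocol*

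**What the plan says.** Four statements in the protocol bear on this.

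- **Age of eligibility values.** Section 4.2.1, item 9: "Patients must meet the following adequate organ and bone marrow function within 21 days prior to inclusion". The list covers neutrophils, platelets, haemoglobin, bilirubin, transaminases and creatinine clearance.
- **Age of baseline blood values.** Section 4.1, under what is due at inclusion: "blood- and urine values within 2 weeks before study start".
- **Platelet transfusion.** Item 9: "Platelet transfusions to help patients meet eligibility criteria are not allowed within 3 days before study enrollment". Section 4.1 fixes the reference day: "The study patient is considered enrolled on first day of study protocol treatment".
- **Red-cell transfusion.** The haemoglobin bullet of item 9: "the most recent RBC may not have given within 7 days prior to obtaining screening Hb".

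Table 1 also schedules haematology within 5 days before day 1 of every cycle, including cycle 1. No section says that this sample must meet the item 9 thresholds.

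**The concern.** There are two separate problems.

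First, the two age limits apply to overlapping blood values and differ. A site working from the eligibility list and a site working from the procedures section can reach different decisions on the same patient. A monitor checking inclusion criteria, as section 8 requires, has no stated basis for choosing between them.

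Second, the platelet rule is aimed at transfusions given so that a patient qualifies, but its only operative limit is measured from the first dose. A transfusion raises the count that is drawn after it, so the interval that matters is the one before the sample. The haemoglobin bullet is built that way and the platelet bullet is not. As written, a patient whose own count is below 75 × 10⁹/L can qualify on a supported count without breaking any rule.

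At stake are consistent eligibility across sites and a platelet criterion that does what it says. Platelets are of some interest here because section 1.4.2 lists thrombocytopenia among carfilzomib's most common side effects, and safety is part of the primary objective in section 2.1.

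**Working it through.** The protocol gives no figure to reproduce on this point. The check is a count of days.

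**Inputs**
- Age limit in item 9: 21 days before inclusion.
- Age limit in section 4.1: 2 weeks, that is 14 days, before study start.
- Platelet-transfusion ban in item 9: 3 days before enrolment.
- Enrolment in section 4.1: first treatment day.
- Assumption: inclusion and study start are also the first dose, called day 0. The protocol defines neither term.

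**Step 1: the two windows.** 21 − 14 = 7. Values from days -21 to -15 meet item 9 and breach section 4.1. Values from days -14 to -1 meet both. If inclusion comes before the first dose, a value valid under item 9 can be more than 21 days old at dosing.

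**Step 2: days on which a transfusion is not banned.** The ban covers days -3, -2 and -1.
- 21-day window: 21 − 3 = 18 days uncovered.
- 14-day window: 14 − 3 = 11 days uncovered.

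**Step 3: the same question by day of the count.** For a count on day c, the three preceding days are c−1, c−2 and c−3. The ban reaches at least one of them only if c−1 ≥ −3, that is c ≥ −2.

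| Count day | Preceding 3 days | Covered by the ban |
|---|---|---|
| -5 | -6, -7, -8 | 0 of 3 |
| -4 | -5, -6, -7 | 0 of 3 |
| -3 | -4, -5, -6 | 0 of 3 |
| -2 | -3, -4, -5 | 1 of 3 |
| -1 | -2, -3, -4 | 2 of 3 |

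Every count day earlier than -5 also has 0 of 3 covered. The totals are:
- 21-day window: no cover on 19 of 21 count days, partial on 2, full on none.
- 14-day window: no cover on 12 of 14 count days, partial on 2, full on none.
- If a transfusion on the day of the draw is also considered, the days with no cover are 18 of 21 and 11 of 14.

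**Step 4: a case that passes every rule.** Platelet transfusion on day -10, count at the threshold on day -9, first dose on day 0. The count is 9 days old, so it meets both limits. The transfusion is 10 days before enrolment, so it is outside the ban. The sample was nevertheless drawn one day after the transfusion.

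**Step 5: whether the pre-cycle-1 sample closes the gap.** Table 1 allows that sample up to 5 days before day 1. Even if it were made binding, the table above shows no cover for counts on days -5 to -3. Moving the reference point is therefore the change that closes the gap.

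**Step 6: after re-anchoring.** If the same 3-day interval were counted back from the sample, all three preceding days would be covered on every count day, 21 of 21 or 14 of 14. The length of 3 days is used here only because it is the protocol's own figure.

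**The case against.** The strongest reply is that the practical effect is small, and much of it stands.

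- **The windows can both be met.** A value no more than 14 days old satisfies item 9 and section 4.1. Section 4.1 can also be read as describing the baseline work-up, since it lists marrow and imaging alongside the blood values. An outdated count qualifies only where item 9 is applied alone. This stands, and makes the window conflict a matter of reconciliation. It does not touch the transfusion gap, which remains under the 14-day limit.
- **A fresh count will be available.** Table 1 gives the investigator a recent count before the first dose. This lowers the risk, but no text makes it an eligibility check, and Step 5 shows that it would not be enough alone.
- **The transfusion would be visible.** Section 5.4 requires blood products to be recorded, with concomitant therapy collected from consent. This allows the cases to be found afterwards but does not make them ineligible.
- **The safety reading is protected.** A reader might infer that supported entry counts would distort the trial's safety conclusion. The protocol does not support that. The only numerical safety threshold, in section 9.2, concerns non-haematological events of grade 3 or higher. Section 7.1 counts only new or worsening conditions as adverse events, and section 9.3 records the baseline platelet count.
- **The response rate is untouched.** Platelet count plays no part in the Appendix 5 response criteria.

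A reader might also infer that the platelet threshold fails altogether. That goes too far: it still excludes every untransfused patient below it. The gap needs a particular sequence of transfusion, qualifying draw, and dosing more than 3 days after the transfusion.

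**Conclusion.** The point holds in two parts. The age limits of 21 days and 2 weeks conflict for values from days -21 to -15 and need to be reconciled. The platelet-transfusion ban is measured from the wrong event, which leaves about 11 days uncovered under the 14-day limit and 18 under the 21-day limit. The transfusion gap is the more important part, because no way of resolving the window conflict removes it.

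The day counts assume that inclusion, study start and first dose fall on the same day. The protocol gives no rate of platelet transfusion before entry, so the number of affected patients is unknown and may be zero; each would be 1/40 = 2.5% of the planned sample. No sample-size or precision figure changes. A reader might expect an effect on the per-protocol analysis, but section 9.2 does not tie that analysis to screening windows, so this cannot be claimed. The gain from correcting the text is consistent eligibility and a platelet criterion that matches its stated purpose.

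**What to change.** Make two changes in an amendment.

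1. State one age limit for eligibility blood values, with one defined reference day, and use it in both section 4.1 and item 9.
2. Reword the platelet rule so that the transfusion-free interval is counted back from the qualifying platelet sample, as the haemoglobin rule already does.

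The sponsor should set both lengths. Optionally, state whether the pre-cycle-1 sample already in Table 1 must meet item 9.

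The cost is about two sentences and no additional scheduled sample. The downside is an occasional re-draw or screen failure.
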